Ten Green top tubes (each 10ml/tube – sodium heparin tubes preferred) should be collected prior to the start of pre-surgery Day 1 (pre-dose) and prior to morning abemaciclib dose on day of surgery. Blood samples for immunologic assays should be shipped (along with the fresh-preserved tumor tissue) via FedEX for overnight delivery directly to UCLA as described in Table 9.2.

Cohorts 1 & 2 Plasma Pharmacokinetic (PK) Samples:

Cohort 1 Pre-Surgery/Surgery

4mL blood should be collected in purple-top EDTA vacutainer (Becton Dickinson Catalog # 367861 or 367844, Franklin Lakes, NJ) prior to start of pre-surgery Day 1 (pre-dose), pre-surgery Day 8 (pre-dose), and on day of surgery at time of tumor resection. All samples should be prior to morning abemaciclib dose.

Cohort 2

For all Cohort 2 participants, 4mL blood should be collected (in purple-top EDTA vacutainer (Becton Dickinson Catalog # 367861 or 367844, Franklin Lakes, NJ) at C1D1 (pre-treatment), C2D1, C3D1 and C4D1(if a participant comes off study treatment prior to C4D1 visit, then an end of treatment sample should be drawn). All samples should be prior to morning abemaciclib dose.

Handling of Specimen(s)

- Obtain venous blood by standard phlebotomy technique from a peripheral access point. NOTE: Suggest using a minimum 18G needle to avoid sample hemolysis.
- Fill-up the tubes as much as possible until blood flow stops.
- GENTLY invert each tube several times (8-10 times) immediately after collection to avoid sample hemolysis.
- Place samples immediately **on ice** after collection; samples must be processed **within 20 minutes**.

Processing instructions

- 1. Invert sample 8-10 times immediately before processing.
- 2. Place the sample(s) on ice or in a refrigerator and separate the **plasma within 60** minutes of collection at 1,500 2,000 x g for 10 minutes in swinging bucket (SW) or 15 minutes in a fixed angel (FA) rotor at 4°C in a refrigerated centrifuge. Make sure that the centrifuge reaches speed and is maintained throughout the entire spin.
- 3. Carefully remove tube from centrifuge.
- 4. Using a pipette, transfer equal aliquots of plasma into 2 labeled 2 mL cryovials, not exceeding 1.5 mL per cryovial.
- 5. Label samples as Abemaciclib PK, including protocol number (16-383), unique patient ID (assigned by the consortium), initials, date of collection, draw time, and time point.
- 6. Store plasma samples at -70°C or below until shipment or transfer to OSU.

Plasma PKs will be batch shipped when requested by the DFCI Coordinating Center.

Preparing the shipment

E-mail the DFCI Coordinating Center at [contact] at least 24 hours prior to shipment of samples to confirm the receiving lab is aware of the shipment.

Samples should be stored in cardboard boxes (5 1/8" x 5 1/8" x 2", LxWxH).

- Organize the samples by patient and timepoint in the box.
- Do not store in plastic bags (they break on dry-ice and labels will detach).
- A copy of each of the PK sample collection forms for the respective patients or a sample list should be included with each shipment. To prevent problems with illegible writing on tubes, consider numbering them (in addition to sample label) and numbering samples on the sample sheet.
- Note the study number, PI, and the drugs used/to be measured.
- A name, phone number, and email address should be included with samples so that receipt can be acknowledged.

Shipping

- All samples should be shipped via overnight express courier in insulated containers with enough dry ice to maintain the samples in a frozen state.
- Tissue PK samples should be sent on Monday through Wednesday (never on Thursday. Friday, weekends, or days prior to a holiday) to:

The OSUCCC Pharmacoanalytical Shared Resource Attn: [name] [name] [contact]

[contact]

Email: [contact]

Upon shipment, send a notification with tracking number to the DFCI Coordinating Center at [contact] and the OSUCCC Pharmacoanalytical Shared Resource at [contact]

Archival Tissue Samples for Screening and Correlative Studies

Guidelines for submission of archival tumor tissue and for PD and tumor antigen presentation and microenvironment correlative studies at DFCI:

- A memorandum indicating the study, the date of submission, name of study site submitting the tissue, and a list of contents. The DFCI Coordinating Center will supply a template memorandum to sites at the time of the SIV or upon request.
- Include copy of the pathology, surgical, and genomic profiling/sequencing reports for the sample being submitted

• Email the DFCI Coordinating Center at [contact] at least 24 hours prior to shipment of samples to confirm the receiving lab is aware of the shipment.

Samples should be sent on a Monday through Thursday (never on Friday, weekends, or days prior to a holiday) to:

[name] (attn.: Adult Path CRC)
Dana-Farber Cancer Institute
Center for Molecular Oncologic Pathology - JF215B
[name]
Ph [contact]

Upon shipment, send a notification with tracking number to the DFCI Coordinating Center at [contact]

Guidelines for submission of archival tumor tissue for immunologic correlative studies at UCLA:

- FFPE slides from archival tissue should be cut and submitted when requested by the DFCI Coordinating Center, when study recruitment has ended. Ship slides in a plastic slide holder/slide box. Place a small wad of padding in top of the container in order to avoid slides breaking during shipping and handling process.
- Complete the provided UCLA Brain Tumor Research Lab memorandum indicating the study, subject ID assigned at registration, date of submission, name of study site submitting the tissue, and a list of contents.
- The DFCI Neuro-Oncology Coordinating Center will provide supplemental Sample Collection & Shipping Guidance to sites at the time of activation or upon request.
- Include a copy of the pathology and surgical report for the sample being submitted
- An email is to be sent before each shipment to the UCLA Brain Tumor Research Lab at [contact] and the DFCI Coordinating Center at NeuroOnc [contact] indicating what is being shipped and when.
- Please note that the submitting institution is responsible for the costs of shipping and handling.
- Ship slides to:

[name]. C/O [name] [name] [name]

[contact]

Email: [contact] and [contact]

Upon shipment, send a notification with tracking number to the DFCI Coordinating Center at NeuroOnc [contact] and UCLA at [contact]

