3.1 Eligibility Criteria

All participants must meet the following criteria on screening examination to be eligible to participate in the study:

- 1. Participants must be able to understand and willing to sign a written informed consent document.
- 2. Participants must be able to adhere to the dosing and visit schedules and agree to record medication times accurately and consistently in a daily diary.
- 3. Participants must be at least 18 years old on day of signing informed consent.
- 4. Participants must have a Karnofsky Performance Status (KPS) \geq 60 (see Appendix A).
- 5. Participants must be able to swallow tablets.
- 6. Participants with a prior or concurrent malignancy whose natural history or treatment does not have the potential to interfere with the safety or efficacy of the trial are eligible.
 - NOTE: consultation with the Overall PI is highly recommended if enrollment of a participant with a prior or concurrent malignancy is being pursued.

Nature of illness and treatment history

- 7. Participants must undergo central pathology review to histologically confirm the diagnosis of glioblastoma, IDH-wildtype; glioblastoma variants; or astrocytoma, IDH-mutant, WHO grade 4 (1 unstained slide or 1 H&E slide must be submitted to and reviewed by a pathologist at the DFCI Coordinating Center prior to enrollment of the participant for central pathology review).
- 8. To be eligible for the study all participants (Cohort 1 and 2) are required to provide genomic profiling data from assays performed in a CLIA-certified lab. A sequencing-based assay is required and must include reporting of the RB1 gene in explicit terms within the report. Only sequencing assays that include coverage of *all* exons of the RB1 gene are able to be utilized (most commonly called a targeted exome assay; e.g. Oncopanel, Impact, FoundationOne). In addition, patients must provide a report of copy

assessment which reports status of RB1. The reporting may be from a copy array (ideally Oncoscan SNP array or Agilent array CGH) or can also be from sequencing assay if copy status is explicitly provided with quantitative information regarding the status of relevant genes. Specifically, the reporting should provide the following information with respect to relevant biomarkers required for enrollment to the study as listed below.

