9.1 Biomarker Studies from Any Prior Surgery

Eligibility for registration will be dependent on prior tumor being profiled by genomic methods that are sufficient for determination of the copy and mutation status of CDKN2A/B/C, RB1, and CDK4/6. Data can be generated from any prior tumor surgery. This data will not be generated as part of the trial process but will be pre-existing data. All data must be performed in a CLIA-certified laboratory. Central molecular pathology review will be performed and may include reports or raw data as needed to determine the status of relevant loci. Commonly used tests include:

- 1. OncoCopy Whole Genome Array CGH (DFCI/BWH)
- 2. OncoPanel Targeted Exome Sequencing (DFCI/BWH)
- 3. FoundationOne testing (Foundation Medicine)
- 4. Other sequencing and copy data (e.g. TGEN)
- 5. IMPACT sequencing and copy (MSKCC)

Data will be evaluated for:

1. Presence of CDKN2A, CDKN2B, CDKN2C loss equivalent to a loss greater than 1 copy of any one or more of these genes. Entry based on single copy loss will be allowed only in the event of a concurrent SNV present which is deemed likely damaging/inactivating by literature and database review.

AND

2. Absence of any copy, SNV, indel, or other aberration deemed likely inactivating in the RB1 gene. These would include non-sense mutations with truncation of protein, or homozygous (>1 copy) loss by copy analysis.

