9.2 Laboratory Correlative Studies

Correlative studies and tissue required for these are mandatory for all participants with the exception of specified imaging studies.

Correlative study time points are included in Section 10 (Required Activity Calendar).

NOTE: Study Sponsor, or his/her designee, may ultimately opt to not pursue analysis of one or more of the correlative studies specified in the protocol if the study is not positive and/or the data gained from the analysis is no longer believed to be helpful.

Cohort 1: In this cohort, patients with recurrent GBM will receive drug for 10-14 days prior surgery, abemaciclib should be taken as close to a 7AM – 7PM schedule as possible during pre-

surgery cycle. The last dose should be on the day of surgery 1-3 hours prior to surgery and tumor removal.

During surgery, tumor tissue and plasma will be collected simultaneously. Planned analyses for resected tumor tissue as follows:

- 1) Frozen tumor samples and plasma samples will be evaluated for drug concentration using liquid chromatography tandem mass spectrometry (LC-MS/MS) to derive a tumor/plasma ratio. Tumor concentration will be compared to plasma drug concentrations to determine if therapeutic levels of abemaciclib can be achieved in both enhancing and non-enhancing tumor.
- 2) Frozen tumor samples, archival and study surgery FFPE tumor tissue will be evaluated for drug target pathway dysfunction and for pharmacodynamic alterations of signal transduction molecules relevant to the response to abemaciclib. Tumor tissue will be analyzed by IHC and proteomics studies for pRb (S807/811), proliferation (e.g. Ki-67), and apoptosis (e.g. cleaved caspase 3) to determine if abemaciclib can achieve a pharmacodynamic effect in enhancing and non-enhancing tumor tissue. These data will be compared to similar analyses performed on tumor tissue not exposed to abemaciclib obtained from each participant's prior surgery, and from tumor specimens from untreated glioblastoma patients who undergo reoperation as part of another ongoing study (ABTC 1301: MLN0128 in recurrent glioblastoma).
- 3) Fresh-preserved tumor tissue and/or whole blood will be evaluated for the drug's immunostimulatory effects based on the following immunological assays:

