9.2.1 DFCI/BWH Testing of Pre-Post Treatment Tumor Tissue

An example of the DFCI prescreening results that may be generated prior to trial entry is described below. In addition, all Cohort 1 on surgery samples will be tested post-treatment tissue using these same assays for comparison to pre-treatment tissue. DFCI FFPE tumor tissue from the participant's surgery prior to enrolling onto the study or Cohort 1 post-treatment tissue will be genotyped with the clinically validated OncoPanel targeted exome sequencing for 300 cancer causing genes and whole genome OncoCopy Agilent array comparative genomic hybridization at 1M probe resolution, and the results correlated with outcome. Both assays are performed in the CLIA-certified laboratory at the Dana-Farber/Brigham and Women's Cancer Center, Center for Advanced Molecular Diagnostics (CAMD).

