9.2.3 Immunohistochemistry Correlates for Cohort 1 Patients

Tumor from all patients will be evaluated by IHC for PD (including the levels of pRB1, CC3, Ki67, and other markers of abemaciclib), tumor microenvironment, as well as immunologic changes in pre or pre-post treatment pairs. These studies will require a total of 17 IHC unstained plus slides cut at 5um thickness (Cohort 1 and 2, archived and study surgery). Ten slides should be sent to [name] at DFCI and 7 slides (on Superfrost Plus glass slides) should be sent to [name] at UCLA. This is for correlation only and is not utilized for trial entry/screening.

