13. STATISTICAL CONSIDERATIONS

13.1 Study Design

This will be an open label Phase II trial in participants with recurrent GBM. Cohort 1 and Cohort 2 will enroll concurrently. In Cohort 1, to ensure that adequate abemaciclib penetrates into the tumors and inhibits cellular proliferation, 15 participants with recurrent GBM who require reoperation will be treated with abemaciclib prior to surgery. After recovery from surgery, participants will receive abemaciclib until disease progression or the development of unacceptable toxicities. In Cohort 2, participants will receive abemaciclib without undergoing prior surgery. The two cohorts will be analyzed separately.

In Cohort 1 we will attempt to characterize the pharmacokinetic (PK) uptake of abemaciclib in brain. A single-time point brain-to-plasma ratio will be calculated for each participant with a paired plasma and brain sample, followed by a descriptive statistical analysis (mean, SD, CV% or median (range)). In addition, both a naive pool strategy of all brain samples as well as a non-linear mixed effect approach will be explored in an attempt to provide a better estimate of time-course of brain uptake, the total brain exposure over a dosing interval (AUC0-24) and the brain-plasma tissue partitioning coefficient (Kpt).

Cohort 1 will also assess for pharmacodynamic (PD) evidence of target inhibition in brain tissue. We will evaluate tumor tissue after treatment with abemaciclib for reduced RB1 signaling,

cellular proliferation, and increased cell death by immunohistochemistry for pRB1, Ki67, and cleaved caspase 3. The IHC effects will be evaluated by pathologist manual scoring of each marker as well as morphometric techniques to determine change relative to pre-abemaciclib biopsy which will also be stained. These results will be compared to a group of 15 patient samples who received treatment only with standard of care TMZ and RT. Results of the two cohorts will be compared statistically to determine whether significant changes are noted.

The primary goal of Cohort 2 is to determine the therapeutic efficacy of abemaciclib as measured by PFS6. Treatment duration will be measured in 4-week cycles. Participants will remain on treatment until tumor progression, as long as there are no unacceptable toxicities. Responses will be assessed by clinical examinations every 4 weeks and MRI scans every 8 weeks.

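### Cohort 1 reads target inhibition from phospho-Rb with no total-Rb measure named, and no rule uses the planned on-study RB1 retest to qualify it, so Rb loss could be read as a drug effect

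*Combined protocol and SAP*

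**What the plan says.** Section 1.3.1 makes the effect on phospho-RB (S807/811) a Cohort 1 secondary objective, together with Ki67, CC3 and p21. Section 9.2, item 2, gives the laboratory plan: "Tumor tissue will be analyzed by IHC and proteomics studies for pRb (S807/811), proliferation (e.g. Ki-67), and apoptosis (e.g. cleaved caspase 3"). Section 13.1 repeats it as evidence of target inhibition: "We will evaluate tumor tissue after treatment with abemaciclib for reduced RB1 signaling", followed by "cellular proliferation, and increased cell death by immunohistochemistry for pRB1, Ki67, and cleaved caspase 3". Section 9.2.3 leaves the list slightly open, "including the levels of pRB1, CC3, Ki67, and other markers of abemaciclib". Total Rb is not named in any of these places, nor in 2.5, Table 9.2 or 13.4. Rb protein staining appears only in 1.1, as one way to document intact RB before enrollment.

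On RB1 status at entry, section 9.1 says: "Data can be generated from any prior tumor surgery". Criterion 11 in section 3.1 likewise lets the Cohort 1 archived tissue come from any surgery.

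On RB1 status at the study surgery, section 9.2.1 says: "all Cohort 1 on surgery samples will be tested post-treatment tissue using these same assays for comparison to pre-treatment tissue". It also says: "Cohort 1 post-treatment tissue will be genotyped with the clinically validated OncoPanel targeted exome sequencing for 300 cancer causing genes", alongside whole-genome array CGH. Criterion 8 in section 3.1 gives OncoPanel as an example of an assay covering all RB1 exons ("most commonly called a targeted exome assay; e.g. Oncopanel, Impact, FoundationOne"). Section 9.2 further plans exome and RNA sequencing of study-surgery tumor.

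For analysis, 13.4 describes the pharmacodynamic results mainly descriptively, before against after. Section 13.1 adds a statistical comparison with 15 samples from patients given only temozolomide and radiotherapy. Section 2.5 describes a similar reference group with n=10, and 9.2 names reoperated patients from another study.

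**The concern.** A phospho-specific signal depends on two things: how much Rb is present and what share of it is phosphorylated. A CDK4/6 inhibitor should lower the share. Loss of the protein lowers the amount. From pRb alone the two look the same.

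The pair being compared may span a first or second relapse and intervening therapy, so Rb status can change between the archived sample and the study surgery. If it does, the error runs in the wrong direction. Section 2.1 reports that cell lines with homozygous Rb inactivation were completely resistant to CDK4/6 inhibition, so the tumor in which the drug has least to act on would show the largest fall in pRb.

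This bears on the purpose of the cohort. Section 2.4 keeps Cohort 1 open, after the limited Cohort 2 result, partly to understand why the drug has limited activity. That requires separating a tumor whose target was inhibited without benefit from a tumor whose target was absent. The plan collects genomic data that would help, but it does not say they will be used for this.

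**Working it through.** The plan states no effect size, variance, alpha or power for pRb, so there is no figure of its own to reproduce. The check has three steps.

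**1. Is Rb measured or used at the study surgery?**

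| Item | Where | Finding |
|---|---|---|
| Total Rb on study-surgery tissue | 1.3.1, 2.5, 9.2, Table 9.2, 9.2.3, 13.1, 13.4 | Not named (9.2.3 allows unspecified other markers) |
| RB1 genomics on study-surgery tissue | 9.2.1; also 9.2 | Planned for all Cohort 1 surgery samples |
| Rule linking that RB1 result to pRb | 9.2, 9.2.1, 9.2.3, 13.1, 13.4 | None |
| Certainty that the retest is done | 9.2 note | The sponsor may drop correlative analyses |

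So the data that could qualify pRb are planned, and the rule that would use them is missing.

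**2. What does Rb loss do to the readout?** Treat signal as proportional to content (an idealization for staining). Let R be the amount of Rb and f the phosphorylated fraction, with 0 for the archived sample and 1 for the study sample.

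- Change in pRb = (R1 × f1)/(R0 × f0) − 1.
- No drug action (f1 = f0) and complete loss (R1 = 0): change = −100%.
- No drug action and half the protein left (R1 = 0.5 × R0): change = −50%.
- Change in pRb relative to total Rb = f1/f0 − 1. This is 0 in the half-loss case, as it should be. It is undefined when R1 = 0, so a completely lost tumor has to be listed separately and not given a ratio.

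**3. How far does the mean move?** Let n = 15 evaluable pairs (sections 5.2 and 13.3), let k tumors be fully Rb-lost (an assumption), and let the mean change in the others be m, in percentage points.

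- Mean over all pairs = [(15 − k) × m − 100 × k]/15.
- Shift caused by the lost tumors = −k × (100 + m)/15.
- With no drug effect in the others (m = 0): k = 1 gives −100/15 = −6.7 points, k = 2 gives −13.3, and k = 3 gives −20.0.
- If m is negative because the drug works, the shift per tumor is smaller, so 6.7 is the largest value for m at or below 0.
- If a tumor loses half its Rb, the m = 0 shift is 50/15 = 3.3 points.

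The documents give no probability p of losing Rb between samples. The chance of at least one such tumor among 15 is 1 − (1 − p)^15:

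| Assumed p | At least one of 15 |
|---|---|
| 1% | 14% |
| 2% | 26% |
| 5% | 54% |
| 10% | 79% |

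**The case against.** **The plan already tests RB1 at the study surgery.** This is correct. A reader of the pRb passages alone might infer that Rb status is never rechecked; section 9.2.1 shows that it is, with an assay that reads RB1. For the same reason it is too strong to say that an Rb-lost tumor would necessarily be scored as a drug effect, because genomic loss should be visible in planned data. What remains is that nothing commits the analysis to look. Genomics also does not measure protein: loss without a detectable genomic change, or confined to the stained area, would be missed.

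**The control comparison handles natural loss.** In part. Controls sampled before and after temozolomide and radiotherapy also span treatment and time, so average drift may cancel. That is a statement about group means. It does not show which treated tumor lost Rb, and no Rb criterion is stated for the controls, so equal loss in the two groups is itself an assumption.

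**A reader might infer a known inflation of the false-positive rate.** The documents do not support one. The inflation could be computed for a one-sample paired t-test, but the plan names no such test. For the between-group comparison in 13.1, a simulation of change in 15 treated tumors against 10 or 15 controls (Welch t-test, assumed SD 30 points, the same assumed loss probability of 0 to 3 in 15 in both groups) rejected at about 5% throughout. No false-positive figure is therefore claimed.

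**Single-copy RB1 loss at entry adds little.** Agreed where it is already present in the archived sample, since it then affects both members of the pair. It matters only if a further event follows.

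**The marker list is open, and Ki-67 is read on the same tissue.** Total Rb is not excluded, but an unnamed marker is not a plan. Ki-67 is a partial cross-check: when it disagrees with pRb, the reason stays ambiguous without total Rb.

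**pRb is a secondary objective.** True; the primary objective is tumor drug concentration. This limits the weight of the point.

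**Conclusion.** The concern holds in a limited form. pRb carries the target-inhibition reading without a named total-Rb measure, and no rule uses the planned RB1 retest to qualify it. A tumor that lost Rb after its archived sample could therefore be read as a pharmacodynamic response. The harm is misclassification of individual tumors and a shifted descriptive mean: up to 6.7 points per fully lost tumor among 15, assuming complete loss, a signal proportional to protein, and no drug effect in the other tumors. How often this would happen cannot be taken from the documents, and the range shown is illustrative. The Cohort 1 primary objective is unaffected. The change is worth making because the cohort is meant to explain limited activity and most of the data needed are already planned.

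**What to change.** In 9.2 item 2, 9.2.3 and 13.1, pre-specify the following:

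1. A tumor whose on-study OncoPanel or array CGH shows RB1 inactivation, by the rule in 9.1, is listed separately and left out of the pRb target-inhibition summary. Results are shown both with and without such tumors.
2. Where slides or proteomic material allow, pRb is also reported relative to total Rb in the same specimen, before and after treatment.
3. The same handling applies to the control samples where RB1 data exist.

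The first item uses assays already planned; it does mean keeping the RB1 retest even if other correlatives are dropped under the note in 9.2. The second adds one stain on tissue already collected, or one protein in the proteomic list. The downside is a possibly slightly smaller evaluable number for pRb.
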